5. PROCEDURES EXPECTED AND INFORMATION COLLECTED

Enrollment procedure

Adult patients of both sexes who belong to pain therapy centers with a diagnosis of Chronic Pain (pain that lasts > 12 weeks), regardless of the etiology, modality and age of onset, will be considered eligible for enrollment.

It will be possible to enroll patients during their first visit (FIRST ANESTHESIOLOGICAL VISIT), or during a check-up visit (ANESTHESIOLOGICAL CHECK-UP VISIT) or during a scheduled hospitalization for pain procedures (ORDINARY OR DAY HOSPITAL ADMISSION)

Patients will be asked to join the study after having been informed in detail (also with the aid of a written information form) of the objectives of the project, as well as the methods with which these objectives will be pursued. Participants will be informed about the lack of informative feedback regarding the results of future clinical evaluations: the results of any research originating from the register, in fact, will not be delivered to the participants themselves. The subject who freely accepts will authorize the inclusion of their data in the project by signing the informed consent form of which they will receive a copy. It will also be clearly explained in the information sheet attached to the informed consent that each participant will have the possibility of withdrawing their participation from the study at any time, without providing any reason and without this jeopardizing the doctor-patient relationship with the specialists involved in the project.

Patients will be informed by the manager of the patient's pain center or the principal investigator for the center (assuming this is not the same individual).

The doctor will complete the electronic CRF after evaluating the patient and classifying him according to the criteria of the IASP (International Association for the Study of Pain) in terms of primary or secondary chronic pain. In the case of a patient enrolled during a check-up or during hospitalization, all data relating to the time in which the patient is in care at the center, the

invasive procedures previously undertaken, the drugs prescribed, will be collected. Retrospective data (only for patients already being treated at the center) will be collected according to a predefined group (e.g.: the patient has been in the care of the center for: > 5 years; from 1 to 5 years; from 1 year to 6 months; from 3 to 6 months; < 3 months).

[figure not shown]
Follow-up procedure

Once enrolled, the patient will be followed prospectively until the end of enrollment. At each visit it will be possible to retrieve the patient's chart and fill in the data relating to the intensity of pain and the treatments undertaken. It will also be possible to modify or add an etiological diagnosis in forms of secondary chronic pain. There is no limit to the number of follow-ups for each patient as long as the database is active (3 months from the date of enrollment of the last patient, considering a 12-month active enrollment expected for this study).

Data gathered

The activities of the registry do not replace routine diagnostic tests or visits to your doctor. The data collected by the registry will include relevant demographic data of the patient, comorbidities, the duration of the pain (> 5 years; from 1 to 5 years; from 1 year to 6 months; from 3 to 6 months), the type of pain, the location of the pain, the intensity of the pain (Brief Pain Inventory- Severity (BPI-S) and pain interference in daily activities (Brief Pain Inventory- Interference (BPI-I), treatments received (categorized according to pharmacological therapy, infiltrative therapy, ablative or neuromodulatory therapy, implants), the tests conducted, the number of other medical specialists contacted for the pathology being studied, the professional who sent it to the center. Specifically, the data collected is shown in Attachment 1
In particular, patients will be characterized by:

Type of pain (chronic primary or chronic secondary according to the scheme proposed by IASP)

Location of pain according to the following scheme (multiple options are possible)

- Lower back pain
- Thoracic
- Upper arts
- Lower limbs
- Head/Neck
- Pelvis

Pain Intensity

Brief Pain Inventory-Severity (BPI-S)

Interference with daily activities

Brief Pain Inventory-Interference (BPI-I)

Clinical information related to the pathology

Therapy
Pharmacological
Infiltrative
Implantable

Data collection methods and anonymization

The data collected will be used for scientific and epidemiological purposes. Each data will be created by a participating center and recorded on the SIAARTI Servers via a web application using the RedCap® data management software.

The study data will be collected and managed using the REDCap^{20,21} electronic data acquisition tools made available by SIAARTI. REDCap (Research Electronic Data Capture) is a secure, web-based software platform designed to support data capture for research studies. It provides:

- 1) an intuitive interface for acquiring validated data;
- 2) Controlled channels with customized access privileges for monitoring data manipulation and export procedures;
- 3) automated export procedures for continuous data download to common packages of statistical software;
- 4) procedures for data integration and interoperability with external sources.

Data will be recorded in the e-CRF only after being anonymized using coding procedures described in a separate document, in accordance with applicable data protection laws, including the EU GDPR. The encryption key of the anonymous data which contains the patient's name, surname and date of birth will be archived only in the files of the local site in a register that allows registration and research of the subject.

For each center participating in the project, an account will be created on the REDCap platform. The data will be recorded using an encrypted data connection (HTTPS) of anonymized input via a web browser or mobile app.

To enable data analysis, each patient will be assigned a unique Subject ID (Patient Identification Number).

REDCap is a secure web application for creating and managing online databases. Unauthorized access to data is impossible since access is permitted according to a hierarchical and role-based criterion. Access to REDCap will be allowed only to data collection personnel of the participating centers, according to the methods established by this protocol. These people will keep the information private.

Data management and storage

RedCap management software will be used for data management. The identification of individual patients by name will not be necessary or required at any time. During the collection and processing of data, therefore, all necessary measures will be adopted to effectively establish anonymization. SIAARTI will also take care of data storage. Each participating center can only access the patient data it has generated and registered on the REDCap platform. Each participating center is required to provide periodic ad hoc reports on the data collected.

Data ownership

Individual data provided by a participating center are primarily the property of the center that generated the data. All investigators have the right to access their data at any time. SIAARTI will be co-owner of the data, in agreement with each participating center.

Subsequent use of the data

SIAARTI and the executive committee, on behalf of the investigators, have the right to use all data collected in the database for scientific purposes. The executive committee and the SIAARTI study groups have the right to access the data in the registry, for research purposes after the conclusion of the research project, and with the approval of the SIAARTI Scientific Committee. In any case, the researchers who contributed to the project will be regularly informed about the ongoing study activities and will be given the opportunity to be included among the authors of any publications.

Storage

A copy of the electronic database will be kept at the SIAARTI headquarters and kept for 5 years for subsequent use by SIAARTI and the executive committee.

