- continuously and systematically collect, evaluate, and archive relevant demographic and clinical information on patients belonging to chronic pain treatment centers, making it available for studies and research.
- promote the use of uniform and comparable classification systems, definitions, and records in the structures participating in the database.

- Define the flow of patients referring to pain therapy centers to allow adequate health planning and the priority areas of intervention of the national health plan.

The data collected will facilitate the planning of future studies aimed to:

- define the impact of chronic pain at a local and national level, and its territorial and temporal variations over time, through prevalence and incidence measures;
- identify clinical subtypes, risk factors, predisposing and triggering factors;
- increase knowledge in the field of chronic pain to standardize diagnostic/therapeutic pathways and promote adequate management strategies.

2. Objectives

Primary Outcomes

Identify the profiles of patients belonging to pain therapy centers in terms of:

1. Location and type of pain
2. Prescribed therapies
3. Effectiveness of therapies
4. Time needed to reach the efficacy outcome

Secondary Outcome

1. Evaluate the proportion of patients who reach the outcome of 30 or 50% improvement
2. Evaluate the healthcare resources used in terms of number of visits and time needed to achieve the best outcome (30 or 50% improvement)
3. Identify patient profiles that are related to clinically significant outcomes and the specific treatments performed, plus their intermediate surrogate outcomes in relation to specific patterns

4. Describe the relevant clinical variables in the study population. In particular, the absolute and relative frequencies of those clinical variables relevant to the effectiveness of the treatment will be described, categorized by type of treatment, and the timing of the start of treatment with respect to the onset of pain. The data collected may be used for predictive analyses.

3. Study Design

This is a prospective, multicenter, non-profit observational cohort study. No intervention on patients outside of common clinical practice is envisaged.

The study is divided into three phases.

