4. STUDY POPULATION

The Registry data will be collected by the structures involved in the management of patients suffering from chronic pain, regardless of the cause. It is necessary to keep the inclusion criteria as broad as possible to obtain a real picture of clinical practice at a national level.

Inclusion criteria

- Subjects > 4 years old
- NRS > 4
- Diagnosis of Chronic Pain according to the IASP19 criteria
- Adherence through written informed consent to participate in the study

Exclusion criteria

- Patients suffering from psychiatric pathology or severe cognitive impairment for which the enrolling doctor does not believe it is useful for the purposes of the study
- Patients unable to sign the informed consent

Description of the pathologies being studied

Adult patients will be enrolled, diagnosed with Chronic Pain (pain lasting > 12 weeks), regardless of the etiology, modality, and age of onset.

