6. ENDPOINT

Primary Endpoint

The number of patients referring to the centers, the type of pain, the proportion of patients who reach the clinically significant outcome, the type of therapies prescribed (pharmacological, neuromodulatory or implanted) necessary to achieve the outcome and the number of accesses and the Time in which a clinically significant improvement will be achieved (Change in BPI-s or BPI-I; a reduction of > 30% is considered clinically significant and a reduction of > 50% is considered optimal, the data will be evaluated for each Item).

Secondary Endpoint

1. The effectiveness of the treatments will be described in terms of
 - a. Change in pain intensity according to the Brief Pain Inventory-Severity questionnaire (BPI-S) A reduction of > 30% is considered clinically significant and optimal a reduction > of 50% the data will be evaluated for each Item)
 - b. b. Change in pain interference on daily activities according to the Brief Pain Inventory-Interference questionnaire (BPI-I). A reduction of > 30% is considered clinically significant and a reduction of > 50% is considered optimal; the data will be evaluated for each item)
2. Proportion of patients achieving clinically significant outcomes in relation to baseline characteristics and specific treatments performed and their intermediate surrogate outcomes in relation to specific patterns.
3. Resources used: Number of visits to the center for each patient in a year; Number of ordinary or day hospitalizations for each patient in a year.
4. The clinical variables relevant to the outcome will be described (e.g. type of pain, comorbidities, the time between treatment and clinically significant improvement, type of therapy undertaken - pharmacological, invasive, implant-based)

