8. STATISTICAL ANALYSIS

All enrolled patients registered in the registry will be included in the analyses. A descriptive analysis will be performed on the collected data. In general, qualitative variables will be described using frequency distributions; the quantitative variables will be described by mean and standard deviation if normally distributed, and by median and interquartile range if asymmetrically distributed. As appropriate, statistical tests will be used for exploratory purposes. Treatment effects (Change in BPI-S and BPI-I scores) will be calculated as the ratio of the difference between baseline and follow-up scores to the baseline score. If the data allow it, inferential analysis will be applied on quantitative data (such as: comparison of Student's t means, Fisher's F, etc.), or on qualitative data (such as: chi square, odds ratio, Mann Whitney U, etc.). The prevalence of the different pathologies and the related confidence intervals will be estimated. Detailed statistical analysis plans will be set up in future research protocols that will use this database as a source of data.

Sample Size

Since this is an observational registry, no prior sample size calculation is required. Considering an expected participation of 12 centers, an estimate of 2500 patients included appears reasonable.

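### As written, NRS > 4 also screens patients already in care on their residual pain, which tilts that group's therapy profile toward inadequate response

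*Protocol*

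**What the plan says.** Section 4 (Inclusion criteria) lists NRS > 4 beside age, diagnosis and consent. It ties the threshold to no entry route, time of measurement or pain item. The same section gives the purpose of the criteria: "It is necessary to keep the inclusion criteria as broad as possible to obtain a real picture of clinical practice at a national level".

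Section 5 (Enrollment procedure) says "It will be possible to enroll patients during their first visit (FIRST ANESTHESIOLOGICAL VISIT), or during a check-up visit", and adds scheduled ordinary or day-hospital admissions. Its own eligibility sentence names adults with chronic pain of more than 12 weeks and does not mention the NRS. For patients not at a first visit, time in care, earlier invasive procedures and prescribed drugs are recorded: "Retrospective data (only for patients already being treated at the center) will be collected according to a predefined group". The groups run from under 3 months to over 5 years.

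Section 2 (Primary Outcomes) sets the target: "Identify the profiles of patients belonging to pain therapy centers in terms of" four items. Item 2 is "Prescribed therapies", item 3 the effectiveness of therapies and item 4 the time needed to reach the efficacy outcome. Section 6 defines response: "a reduction of > 30% is considered clinically significant and a reduction of > 50% is considered optimal". Section 8 states: "All enrolled patients registered in the registry will be included in the analyses". The only separate analysis announced is for patients under 18 (Section 3, Setting).

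**The concern.** The same threshold does two different jobs. At a first visit, it selects on severity before the centre has treated the patient. At a check-up or admission after months or years in care, it selects on what the centre's treatment has left behind. A patient brought to 4 or below still belongs to the centre and still has a prescribed therapy, but is not eligible.

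The description of prescribed therapies is at stake. In the in-care group, regimens that leave patients above 4 are over-represented relative to regimens that bring them to 4 or below. If that group is merged with first-visit patients, the result describes neither new referrals nor everyone under care. Analysis cannot undo the selection, because nothing is recorded on patients who were never eligible and Attachment 1 has no pre-treatment score for those already in care.

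**Working it through.** The protocol gives no figure on this point, so there is none to reproduce.

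**Inputs from the protocol.** Entry requires NRS > 4 (Section 4), which on an integer scale means 5 or more. Response is a fall of more than 30% or more than 50% (Section 6). The effect is (baseline − follow-up) / baseline (Section 8).

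**Assumptions.** The NRS is an integer 0-10 score. The response rule, which Section 6 sets for BPI items, is applied to that score. The pre-treatment score b was 5 to 10, and the score f at the check-up or admission is what the threshold is applied to.

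**Enumeration.** A pair (b, f) is a response if (b − f)/b exceeds 0.30 or 0.50. It is eligible if f is 5 or more.

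| b | f with fall > 30% | of these eligible | f with fall > 50% | of these eligible |
|---|---|---|---|---|
| 5 | 0-3 (4) | none | 0-2 (3) | none |
| 6 | 0-4 (5) | none | 0-2 (3) | none |
| 7 | 0-4 (5) | none | 0-3 (4) | none |
| 8 | 0-5 (6) | 5 | 0-3 (4) | none |
| 9 | 0-6 (7) | 5, 6 | 0-4 (5) | none |
| 10 | 0-6 (7) | 5, 6 | 0-4 (5) | none |
| Total | 34 | 5 | 24 | 0 |

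The zero is general. A fall of more than 50% gives f < b/2 ≤ 5, so f is at most 4. For a fall of more than 30%, f < 0.7b, and f of 5 or more needs b > 5/0.7 = 7.14, so b must be at least 8. The five surviving pairs are 8 to 5 (37.5%), 9 to 5 (44.4%), 9 to 6 (33.3%), 10 to 5 (50.0%) and 10 to 6 (40.0%). These are unweighted pairs, not proportions of patients. On the 1-10 item format in Attachment 1, the six pairs with f = 0 drop out of each total, leaving 5 of 28 and 0 of 18.

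**Illustration with assumed distributions.** Take a pre-treatment mean of 6.5 to 7.5 with SD 1.5, limited to 5-10, and a mean reduction of 20% to 40% with SD 30 percentage points. None of these values comes from the protocol. Responders above 30% make up 36-63% of in-care patients before selection and 7-23% of those above 4. Responders above 50% go from 13-33% to 0%. Of the responders above 30%, 9-25% remain eligible.

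**Illustration of therapy mix with assumed control rates.** Two therapies each have 100 in-care patients. If 60% and 20% are at 4 or below, 40 and 80 can enter, and the first therapy's share is 40/120 = 33% instead of 50%. With 50% and 30%, it is 50/120 = 42%. Both shares are for the in-care group only. Adding an equal number of enrolled first-visit patients (120, split 60:60) gives (40 + 60)/240 = 42% and (50 + 60)/240 = 46%.

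**The case against.** A reader might infer that no in-care patient whose therapy works can enter, and that this group consists of treatment failures. The documents do not support that. By the protocol's own rule, a fall from 8 to 5 or from 10 to 6 is clinically significant and still qualifies. Patients in care for under 3 months may have only just started therapy, and relapses enter too. Those admitted for a procedure may have high pain with or without a threshold.

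A reader might also infer that the effectiveness results are invalid. Effectiveness is measured prospectively from enrolment, and no endpoint counts patients controlled at entry. What remains is a restriction of scope: effectiveness in this group refers only to patients with residual pain above 4.

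Applying the threshold at the check-up is the natural reading but is not stated. Section 5 leaves it out, and Attachment 1 records worst, least, average and current pain without saying which is the NRS. This is fair, and it is a reason to reconcile the sections, since centres could apply the criterion differently.

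An entry threshold is also defensible, because low baselines leave little room to improve. On a 1-10 item, a baseline of 1 cannot fall, and a baseline of 2 can fall by exactly 50%, which misses the > 50% mark. That weighs against simply waiving it. Finally, entry mode is already recorded, and separating the groups could be left to an analysis plan. The separation could, but eligibility and the population named in Section 2 are fixed in the protocol.

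**Conclusion.** The point holds in a limited form and should be corrected. Read as written, NRS > 4 applies to every entry route. Applied at a check-up or admission, it excludes every in-care patient with a current reduction above 50%, and it keeps those with a reduction above 30% only for five score pairs starting from 8, 9 or 10. The prescribed-therapy profile of in-care entrants (Primary Outcome 2) is therefore tilted toward inadequate response. Pooling them with first-visit patients does not give the population named in Section 2, nor the real picture that Section 4 asks for.

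The score-pair result rests only on an integer scale, a pre-treatment score of at least 5 and measurement at the enrolment visit. The size of the tilt in actual patients is unknown. The simulated ranges and the 33% and 42% shares depend on assumed values and show direction only.

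**What to change.** Reconcile Sections 4 and 5 by stating when the NRS is taken, which pain it rates and for which entry routes NRS > 4 applies.

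If it applies to all routes, add to Sections 2, 6 and 8 that Primary Outcomes 2 to 4 are reported separately by the entry mode in Attachment 1. General statements on therapy mix and effectiveness should then rest on first-visit patients, and the others should be labelled as in-care patients with NRS > 4 at entry.

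The cost is a few lines of text and no new data field for entry mode. The downside is a smaller set for the main therapy and effectiveness statements. Exempting in-care entrants from the threshold would remove the selection, but it would bring in low baselines with little room to improve, so that choice should be made openly.

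### Past therapies are collected over an open-ended period for in-care patients only and are not marked as past, so they could inflate the primary description of prescribed therapies

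*Protocol*

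**What the plan says.** - **Entry routes.** Section 5, Enrollment procedure: "It will be possible to enroll patients during their first visit (FIRST ANESTHESIOLOGICAL VISIT), or during a check-up visit", or during a scheduled admission.
- **Look-back.** For patients entered by one of the latter two routes, the same section asks for data on their period under the centre's care, and says that "invasive procedures previously undertaken, the drugs prescribed, will be collected". The next sentence restricts this by patient: "Retrospective data (only for patients already being treated at the center) will be collected according to a predefined group". The example of such a group is time in care: "the patient has been in the care of the center for: > 5 years; from 1 to 5 years", and so on down to under 3 months. No limit on the look-back is stated, and the top band is open-ended.
- **Primary outcome.** Section 2 lists "Prescribed therapies" among the primary outcomes. Section 6 puts into the primary endpoint "the type of therapies prescribed (pharmacological, neuromodulatory or implanted) necessary to achieve the outcome", where the outcome is a percentage reduction in BPI scores.
- **Analysis.** Section 8: "All enrolled patients registered in the registry will be included in the analyses". Qualitative variables are described by frequency distributions. The only separate analysis named is for patients under 18 (Section 3, Setting). No split by entry route or time in care is stated.
- **Form.** Section 5 points to Attachment 1 for the data collected. Attachment 1 has a form date, the entry route and the time-in-care band. Its Level 3 therapy list has no past/current mark and no start date. Its only time entry is a number of days for regular use of NSAIDs and COXIBs, which does not place the course before or after enrolment.

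**The concern.** The period over which a therapy can be recorded depends on how the patient entered. A first-visit patient can contribute therapies only from enrolment onward. A patient more than 5 years in care can contribute at least 60 months of earlier procedures and drugs as well. At that patient's enrolment contact, past and current therapies appear to share one list under one date.

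Two things follow. First, if the past entries are counted in the all-patient frequencies, the profile of therapies partly reflects the mix of entry routes and lengths of care, which is not a feature of prescribing. The registry is meant to inform health planning, so a mix effect read as practice would mislead. Second, therapies given before the baseline BPI fit poorly with an endpoint that asks which therapies were needed to achieve a change from that baseline.

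Because the gap lies in data capture, an analysis plan written later could not reliably close it.

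**Working it through.** The protocol gives no figure to reproduce: Section 8 makes no sample size calculation, and 2500 patients is a feasibility estimate. The check compares the ascertainment windows and then illustrates their effect.

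**Windows, from the protocol**

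- Section 3 dates: first enrolment 01/06/2023, last enrolment 01/03/2025, data entry to 01/09/2025. Prospective time per patient is 6 to 27 months, with midpoint (6 + 27)/2 = 16.5 months, or F = 1.375 years.
- Look-back T: 0 for a first visit, and at least 60 months in the top band.

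**Assumptions (none is in the protocol)**

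- Procedures occur at a constant rate r per patient-year, the same for every patient and centre. Range shown: 0.05 to 0.30.
- T = 3 years stands for the 1-to-5-year band and T = 7 years for the band above 5 years.
- In the pooled figures, in-care patients are split equally between those two bands.

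**Formula.** If look-back entries are counted, the share with at least one recorded procedure is 1 − exp(−r(T + F)). Example at r = 0.10, T = 3: 1 − exp(−0.10 × 4.375) = 35.4%.

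| r per year | First visit (T = 0) | 1 to 5 years (T = 3) | Over 5 years (T = 7) |
|---|---|---|---|
| 0.05 | 6.6% | 19.6% | 34.2% |
| 0.10 | 12.8% | 35.4% | 56.7% |
| 0.30 | 33.8% | 73.1% | 91.9% |

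**Pooled frequency.** With in-care share s, it is (1 − s) × first-visit value + s × mean of the two in-care values. At r = 0.10, s = 0.2: 0.8 × 12.8% + 0.2 × (35.4% + 56.7%)/2 = 19.5%.

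| r per year | s = 20% | s = 80% | Prospective entries only |
|---|---|---|---|
| 0.05 | 10.7% | 22.9% | 6.6% |
| 0.10 | 19.5% | 39.4% | 12.8% |
| 0.30 | 43.5% | 72.8% | 33.8% |

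Practice is identical in every cell of a row, so the differences come only from the length of the window. If look-back entries are not counted, T drops out and, at equal F, every time-in-care group has the value in the last column.

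**Can the entries be separated later?** Follow-up forms carry a visit date, so therapies entered after enrolment can be. On an in-care patient's enrolment form they cannot: one date covers the whole list, and nothing on the list says which items are past.

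**The case against.** A reader might infer that the protocol pools past and prospective therapies, so that the frequencies must rise with years in care. The documents do not support that. Section 8 fixes which patients are analysed, not which records count as prescribed therapies. The Section 6 wording, which ties therapies to a BPI response, points if anything toward therapies given after baseline. The artefact is conditional on a counting rule that the protocol leaves open, and such a rule could normally wait for an analysis plan.

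Other points on that side also stand:

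- Entry route and time-in-care band are on the form, so results can be stratified without new data.
- No comparison of therapy frequencies between centres or care-duration bands is planned. Territorial variation is left to future studies.
- Section 2 asks for patient profiles, and an implant already in place belongs in the profile of a patient under care. A first-visit patient's zero for earlier therapy at that centre is a true value.
- The rates above are assumed, and they describe procedures, not drugs.
- A figure in the enrolment procedure is not shown and might hold more detail.

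A reader might also infer from Section 3 that everyone has 6 months of follow-up. That is not assured: the Follow-up procedure in Section 5 keeps the database active for only 3 months after the last enrolment, and both sections also speak of follow-up until the end of enrolment.

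What these points do not answer is the enrolment form. Stratifying by time in care would expose a rise but would not separate past from current therapy within a band. An analysis plan can choose a counting rule only if the data distinguish the categories.

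**Conclusion.** The point holds in conditional form. Three things are firm from the text: look-back applies only to in-care patients, its length varies and has no stated limit, and the Attachment 1 therapy list does not distinguish past from current entries at enrolment. Whether the primary frequencies are distorted depends on a counting rule that the protocol does not state.

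If past entries are counted, the effect can be large. Across assumed rates of 0.05 to 0.30 per year, the pooled frequency at an 80% in-care share is roughly two to three and a half times the prospective-only value (72.8/33.8 = 2.2; 22.9/6.6 = 3.5). These are illustrations under a constant, uniform rate and an assumed patient mix, not estimates for this registry. If past entries are not counted, look-back adds nothing. The correction is still worth making, because it is cheap at data entry and cannot be reliably made afterwards.

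**What to change.** 1. **Form.** Add a field to the enrolment therapy list in Attachment 1, for every entry route, marking each therapy as past (ended or performed before enrolment), ongoing at enrolment (including implants in place), or newly prescribed or performed from enrolment.
2. **Primary description.** State in Section 8 that the prescribed-therapies outcome rests on therapies ongoing at enrolment or started from enrolment. Summarise newly started therapies over one common follow-up window.
3. **Window.** Set its length only after the closing rules in Section 3 and in the Follow-up procedure of Section 5 have been reconciled.
4. **Treatment history.** Report past therapies separately, by the existing time-in-care bands, and do not pool them with the primary description.

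The cost is one extra CRF field, a few sentences in Section 8, and therapy frequencies lower than a pooled count would show. Implants in place stay in the primary profile as ongoing therapy.
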